| Demographics | X | | X | | X |
| Physical examination ^d | X | X | X | | X |
| Vital signs ^d | X | X | X | | X |
| Body surface area (BSA) ^e | | X | | | X |
| ECOG PS | X | X | X | | X |
| EKG | X ^f | | X | | X |
| AE ^d | X | X | X | X | X |
| Concomitant medication | X | X | X | X | X |
| Quality of life ^l | X | | X | | X |
| Laboratory examination | | | | | |

SCHEDULE OF ACTIVITIES

| Item/evaluation time | Screening period ^a | Treatment period | Follow-up period | |
|--|-------------------------------|----------------------|---|--|
| | | Treatment period | Every 8 weeks in 36 weeks until PD ^b | End-of treatment visit |
| Hematology | X | D1 X ^h | D8 | D15 D22 D29 |
| Liver and kidney function, blood electrolyte | X | X ^h | | X X X |
| Urinary pregnancy test ^l | X | | | |
| Study treatment | | | | |
| Apatinib Mesylate Tablets 500mg | | X ^m | X ^m | X ^m X ^m X ^m |
| SHR-1210 200mg Q2W (for 36 weeks) | | X | | X |
| Curative effect | | | | |
| Tumor imaging evaluation | X ^b | | | X ^b X ^b X ^b |
| AE | X ^k | | | X ^k X ^k X ^k |

BSA = body surface area; ECG = electrocardiogram; PD = disease progression;

- The informed consent should be signed within 2 weeks before the medication. Screening evaluation should be completed within 2 weeks before medication.
- The disease was assessed using the same radioimaging techniques (CT scan or MRI), every 8 weeks during the treatment period and every 12 weeks during the follow-up period until the disease progressed, the subjects began follow-up anti-cancer treatment, the end of the study or the subjects died. Disease assessment should include enhanced CT or MRI of the primary tumor site, chest plain CT, ECT whole body bone imaging or whole body PET/CT examination.

- c. Subjects will continue to receive research medication until the disease progresses or unacceptable toxicity occurs. End-of-treatment visits should be conducted within 4 weeks of the last drug administration and adverse events within 4 weeks of the last drug administration should be recorded.
- d. The abnormal changes of clinically significant physical examination results (including vital signs and ECOG physical condition score) should be recorded as adverse events, and PD should not be reported as adverse events.

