6.1. Screening Period

The screening period begins with the signing of the informed consent form and ends with the randomization or screening failure. Termination of this study after signing the informed consent form and prior to randomization will be regarded as screening failure. Subjects with screening failure can be re-screened. They must sign the informed consent form again, re-register and obtain a new subject number at the re-screening. Subjects can only be re-screened once.

Subjects must sign the informed consent form before performing any screening procedure specified in this study. In case routine radiological evaluation has been performed for tumors prior to the signing of the informed consent form, computed tomography (CT), magnetic resonance imaging (MRI) or bone scan does not need to be repeated in screening period as long as they are completed within 28 days prior to the start of study drug (42 days prior to start of study drug is acceptable for bone scan), and meet the requirement for radiological evaluation in this study.

Unless otherwise noted, collection of the following data should be completed within 28 days prior to the start of study drug:

- Obtain the informed consent form signed by the subject;
- Assign subject number (subjects will be assigned a unique number in the study: the subject number reflects the numbering of study sites and numbering of subjects within the same study site; the numbering of subjects shall be in accordance with the sequence in which the subjects sign the informed consent form, for example, 001, 002, 003, etc.);
- Collect demographic characteristics;
- Collect medical history (including history of tumor and past history of other diseases);
- Collect concomitant medications/therapies;
- Collect AE;
- Tumor imaging evaluation: the radiological evaluation prior to the signing of informed consent form and within 28 days prior to the first dose is acceptable, and will be performed based on RECIST v1.1 (evaluated by investigator and BIRC), irRECIST (evaluated by investigator only). All the measurable and evaluable tumor lesions should be evaluated and recorded, including CT scan of thorax, abdomen, pelvis and site of lesions, brain MRI or enhanced CT scan (excluding intracranial metastasis); bone scan should be performed once every 24 weeks and PET/CT can be performed only when clinically indicated;
- Check eligibility criteria.

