7.2. Tumor Imaging Evaluation

7.2.1. Tumor Evaluation Based on RECIST v1.1, and irRECIST.

RECIST v1.1 (investigator and BIRC evaluated), irRECIST (only investigator evaluated) will be used for evaluation of tumor response in this study, see APPENDIX 1 for the evaluation criteria.

The tumor evaluation in screening period (at baseline) should include the enhanced CT scan of thorax, abdomen and pelvis. CT scan requires intravenous contrast agent and will scan the whole liver area, at least including 1) hepatic arterial phase and 2) portal venous phase. Enhanced MRI can be used in case of contraindications for CT contrast agent. The enhanced MRI of the whole liver should at least include 1) hepatic arterial phase and 2) portal venous phase. Cranial enhanced CT or enhanced MRI has to be performed at baseline as well. Systemic bone scan should be performed for subjects with known bone metastasis or suspected bone metastasis (exempted in case bone scan is performed within 42 days prior to randomization), the bone lesions need to be evaluated and followed up after treatment. If clinically indicated, tumors at other sites can be evaluated.

Provision on selection of target lesions: if there are no more than two target lesions in each organ, and the total number of lesions is not more than 5, more organs involved in tumors should be covered as far as possible. At baseline, the number and location of the target lesion, the major diameter of each target lesion (except lymph node) and the minor diameter of lymph node lesion, as well as the sum of diameters of all lesions should be recorded.

The baseline evaluation and post-treatment efficacy evaluation should be performed using the same method and by the same investigator as far as possible. Following

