randomization, the tumor evaluation will be performed once every 8 weeks (56 ± 7 days) in the first 48 weeks, and once every 12 weeks (84 ± 7 days) afterwards. In the absence of a determined progression of the disease, tumor evaluation should be continued, regardless of whether the subject has terminated the study, until the subject dies, withdraws the informed consent, initiates subsequent antitumor therapy or terminated the study by sponsor, whichever comes first. Tumor evaluation during treatment includes CT scan of thorax, abdomen, pelvis and site of lesions; cranial CT/MRI and bone scan can be performed only when clinically indicated. Each tumor evaluation must cover all the target lesions, and all the non-target lesions if there are no special circumstances.

Further guidance and recommendations on image acquisition are provided in the Image Acquisition Guidelines.

When clinically indicated, investigators can perform unscheduled tumor evaluation. Throughout the study, each subject must use the same procedure of radiological examination. Investigators must review the results prior to the next cycle of therapy. The subjects who have achieved remission (complete remission or partial remission) for the first time need to be confirmed through the next scheduled evaluation or repeated evaluation ≥ 4 weeks after the first evaluation. The progression of disease that is suspected as pseudoprogression must be confirmed in subsequent radiological examinations, the time of the radiological examination for confirmation is at least 4 weeks after disease progression is detected or at the next scheduled time point (not exceeding 12 weeks), and prior to the termination of study treatment. Patients who meet RECIST v1.1 criteria for progression will continue to receive tumor evaluation, until progression of disease (in accordance with the irRECIST definition) or end of study treatment, whichever comes later.

Once progressive disease occurs, a physical examination of the subject and imaging confirmation is required at all times, rather than waiting for the next planned imaging examination. If the unplanned imaging findings do not meet the RECIST V 1.1 criteria of progressive disease, follow-up examinations should still be performed on the original date for the next imaging examination, unless the next planned examination is less than 14 days of this one.

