1.2 Specifications by methods of measurements

Measurement of lesions

All measurements should be recorded in metric notation, using calipers if clinically assessed. All baseline evaluations should be performed as close as possible to the treatment start and never more than 4 weeks before the beginning of the treatment.

Method of assessment

The same method of assessment and the same technique should be used to characterize each identified and reported lesion at baseline and during follow-up. Imaging based evaluation should always be done rather than clinical examination unless the lesion being followed cannot be imaged but are assessable by clinical exam.

Clinical lesions: Clinical lesions will only be considered measurable when they are superficial and 10 mm diameter as assessed using calipers (e.g. skin nodules). For the case of skin lesions, documentation by color photography including a ruler to estimate the size of the lesion is suggested. As noted above, when lesions can be evaluated by both clinical exam and imaging, imaging evaluation should be undertaken since it is more objective and may also be reviewed at the end of the study.

Chest X-ray: Chest CT is preferred over chest X-ray, particularly when progression is an important endpoint, since CT is more sensitive than X-ray, particularly in identifying new lesions. However, lesions on chest X-ray may be considered measurable if they are clearly defined and surrounded by aerated lung.

CT, MRI: CT is the best currently available and reproducible method to measure lesions selected for response assessment. This guideline has defined measurability of lesions on CT scan based on the assumption that CT slice thickness is 5 mm or less. When CT scans have slice thickness greater than 5 mm, the minimum size for a measurable lesion should be twice the slice thickness. MRI is also acceptable in certain situations (e.g. for body scans).

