2.5 New lesions

The appearance of new malignant lesions denotes disease progression; therefore, some comments on detection of new lesions are important. There are no specific criteria for the identification of new radiographic lesions; however, the finding of a new lesion should be unequivocal: i.e. not attributable to differences in scanning technique, change in imaging modality or findings thought to represent something other than tumor (for example, some 'new' bone lesions may be simply healing or flare of pre-existing lesions). This is particularly important when the patient's baseline lesions show partial or complete response. For example, necrosis of a liver lesion may be reported on a CT scan report as a 'new' cystic lesion, which it is not.

A lesion identified on a follow-up study in an anatomical location that was not scanned at baseline is considered a new lesion and will indicate disease progression. An example of this is the patient who has visceral disease at baseline and while on study has a CT or MRI brain ordered which reveals metastases. The patient's brain metastases are considered to be evidence of PD even if he/she did not have brain imaging at baseline.

If a new lesion is equivocal, for example because of its small size, continued therapy and follow-up evaluation will clarify if it represents truly new disease. If repeat scans confirm there is definitely a new lesion, then progression should be declared using the date of the initial scan.

While FDG-PET response assessments need additional study, it is sometimes reasonable to incorporate the use of FDG-PET scanning to complement CT scanning in assessment of progression (particularly possible 'new' disease). New lesions on the basis of FDG-PET imaging can be identified according to the following algorithm:

Negative FDG-PET at baseline, with a positive FDG-PET at follow-up is a sign of PD based on a new lesion.

No FDG-PET at baseline and a positive FDG-PET at follow-up:

If the positive FDG-PET at follow-up corresponds to a new site of disease confirmed by CT, this is PD.

If the positive FDG-PET at follow-up is not confirmed as a new site of disease on CT, additional follow-up CT scans are needed to determine if there is truly progression occurring at that site (if so, the date of PD will be the date of the initial abnormal FDG-PET scan).

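### The protocol's imaging lists contradict each other on abdomen, pelvis, brain and bone, so a subject's 6-month progression status can depend on which list is applied at a visit

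*Protocol*

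**What the plan says.** The primary endpoint is the 6-month progression-free rate by RECIST v1.1 (Synopsis; Section 2), so it depends on which parts of the body are imaged and when.

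- **Schedule of Activities, footnote b**, is attached to both the screening and the later imaging cells. It states: "Disease assessment should include enhanced CT or MRI of the primary tumor site, chest plain CT", and continues with "ECT whole body bone imaging or whole body PET/CT examination". Assessment is every 8 weeks on treatment.
- **Section 6.1** lists thorax, abdomen, pelvis, lesion sites and brain at screening. It sets bone scans at 24-week intervals and limits PET/CT to clinical indication.
- **Section 7.2.1, baseline**, requires enhanced CT of thorax, abdomen and pelvis, and adds: "Cranial enhanced CT or enhanced MRI has to be performed at baseline as well". A baseline bone scan is required only where bone metastasis is known or suspected.
- **Section 7.2.1, on treatment**: "Tumor evaluation during treatment includes CT scan of thorax, abdomen, pelvis and site of lesions". Section 6.2 asks for the same regions. Both leave brain and bone imaging after baseline to clinical indication.
- **Appendix 1, section 2.5**: progression includes a lesion found at follow-up in an "anatomical location that was not scanned at baseline is considered a new lesion and will indicate disease progression".

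The baseline windows also differ. Footnote a puts screening evaluation within 2 weeks before medication. Section 6.1 accepts CT or MRI within 28 days and a bone scan within 42 days. Section 7.2.1 repeats the bone-scan allowance ("exempted in case bone scan is performed within 42 days prior to randomization"). Appendix 1, section 1.2, says baseline evaluations are "never more than 4 weeks before the beginning of the treatment".

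**The concern.** Each list could be followed in good faith, and the protocol does not say which governs. Under the Appendix 1 rule, a lesion that existed before treatment becomes on-study progression if its region was skipped at baseline and imaged later. If the region is never imaged, real progression there goes unseen and the subject counts as progression-free.

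The trial is single-arm. It compares an observed rate with fixed values of 37% and 60%, so there is no concurrent control in which the same imaging error would occur and partly cancel. The same status also feeds the stage-1 count. A missed baseline region cannot be recovered once treatment has started.

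**Working it through.** The protocol gives no figure for this point, so there is none to reproduce. The check is a comparison of the texts, followed by an illustration of scale.

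**Step 1. Lists side by side**

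| Source | Applies to | Chest | Abdomen and pelvis | Brain | Bone |
|---|---|---|---|---|---|
| Footnote b | Screening and on study | Plain CT | Not named | Not named | Bone imaging or PET/CT in the assessment |
| 6.1 | Screening | CT | CT | MRI or enhanced CT | Scan every 24 weeks; PET/CT if indicated |
| 7.2.1 | Baseline | Enhanced CT | Enhanced CT | Required | If bone metastasis known or suspected |
| 6.2 | On treatment | Enhanced CT | Enhanced CT | If indicated | If indicated |
| 7.2.1 | On treatment | CT | CT | If indicated | If indicated |

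Footnote b can be satisfied with primary site, chest and bone imaging alone. Choosing PET/CT would bring in abdomen and pelvis, but 6.1 restricts PET/CT.

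**Step 2. Consequences for one subject**

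- Baseline by footnote b with bone imaging, later scans by 6.2 or 7.2.1: an existing abdominal or pelvic lesion is first seen on study and is progression under Appendix 1, 2.5.
- All scans by footnote b with bone imaging: progression confined to abdomen, pelvis or brain is not looked for.
- Baseline by 7.2.1 without a bone scan because no bone metastasis was suspected, later scans by footnote b: an existing bone lesion becomes progression.
- Later scans by 6.2 or 7.2.1 with no clinical indication: bone progression is not looked for.

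The first and third lower the 6-month rate; the second and fourth raise it.

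**Step 3. Bone frequency before 6 months (about 26 weeks)**

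Eight-weekly imaging gives 24/8 = 3 bone assessments by week 24. The 24-week rule gives one. The indication-only rule may give none. Section 1.1.1 names bone as the second most common metastatic site after lung, so this conflict concerns a region where progression is expected.

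**Step 4. Scale (illustration only)**

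Inputs from Section 10.1: continue with at least 6 of 12, 43 in total, null rate 0.37, alternative 0.60. The protocol states no final cut-off. I assume at least 21 of 43, the smallest with exact alpha no greater than 0.05 (20 of 43 gives 0.0779; 21 gives 0.0499).

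P(success | p) = sum over x = 6 to 12 of P[Bin(12, p) = x] × P[Bin(31, p) ≥ 21 − x]

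| Shift in points | Added progression, true 60%: p | P(success) | Hidden progression, true 37%: p | P(false positive) |
|---|---|---|---|---|
| 0 | 0.60 | 0.819 | 0.37 | 0.050 |
| 2 | 0.58 | 0.766 | 0.39 | 0.082 |
| 5 | 0.55 | 0.668 | 0.42 | 0.155 |
| 10 | 0.50 | 0.464 | 0.47 | 0.335 |

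In subjects, these shifts are 0.02 × 43 = 0.9, 0.05 × 43 = 2.2 and 0.10 × 43 = 4.3. One subject is 1/43 = 2.3 points of the final rate and 1/12 = 8.3 points of the stage-1 rate.

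The 0.819 in the zero-shift row is below the stated power of 0.90. That is a separate sample-size matter and adds nothing to this point.

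**The case against.** The best defence is that footnote b sets a minimum in a summary table, while the body sections agree on thorax, abdomen and pelvis both at baseline and on treatment. A careful team would follow the fuller text. Sections 6.2 and 7.2.1 require the same radiological procedure for a subject throughout, and footnote b and Appendix 1, 1.2, ask for the same technique. Section 7.2.1 also refers to Image Acquisition Guidelines that are not available here. This weighs against mixing lists within a subject, so I would not assume that it happens often. However, none of these rules names the regions, and nothing in the protocol ranks footnote b below the body text. The bone conflict lies partly among the body sections themselves, so following the fuller text does not resolve it.

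A reader might also infer more than the documents support:

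- **That footnote b confines imaging to primary site, chest and bone.** It sets a minimum and permits whole-body PET/CT.
- **That results would vary by site.** The trial is single-centre; the dependence is on the list applied to a subject or visit.
- **That the CNS exclusion goes unchecked by imaging.** Sections 6.1 and 7.2.1 both call for brain imaging at baseline; only footnote b is silent.
- **That a 42-day-old bone scan will generate false progression.** The 42-day allowance appears in two sections and reads as a deliberate exception to the general RECIST text. Appendix 1 also says bone scans cannot measure lesions, requires new lesions to be unequivocal and warns about healing or flare.

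**Conclusion.** This is an internal inconsistency and is wrong as written. The region lists and the bone-imaging frequency conflict. Through the Appendix 1 rule on regions unscanned at baseline, the conflict can change a subject's 6-month status in either direction.

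Neither the net direction nor the size can be stated, because the documents give no frequency of abdominal, pelvic, brain or bone-only lesions. The 2, 5 and 10 point shifts and the 21/43 cut-off are assumptions. They show that a change of about one to four subjects in 43 would matter to the decision; they do not show that such a change will occur.

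**What to change.** - Reconcile footnote b and Sections 6.1, 6.2 and 7.2.1 into one list of regions and one bone-imaging frequency. The choice belongs to the investigators and the sponsor.
- State that the baseline assessment must cover every region scheduled for on-study imaging.
- Reconcile the baseline windows: 2 weeks in footnote a, 28 days (42 for bone scan) in 6.1, and 4 weeks in Appendix 1. If the bone-scan window is meant as an exception to Appendix 1, say so there.

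There is no reason to drop progression calls made in a region without a baseline image, since they are valid under Appendix 1, 2.5. Matching coverage at baseline prevents the problem at source.

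The cost is wording in the protocol and, where needed, the imaging guidelines. Some subjects may need a fuller baseline scan than footnote b alone implies.

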1. INTRODUCTION: BACKGROUND AND SCIENTIFIC RATIONALE

1.1. Study Background

1.1.1. Epidemiology and Current Treatment Status of Advanced Osteosarcoma

Osteosarcoma is a malignant tumor arising from mesenchymal tissue, which is highly invasive and prone to hematogenous metastasis in the early stage. The most common site of metastasis is lung, followed by bone. With the development of high-dose methotrexate (HD-MTX)/cisplatin (DDP)/doxorubicin (ADM)/ifosfamide (IFO)-based neoadjuvant/adjuvant chemotherapy and limb salvage technology, the disease-free survival and overall survival of patients with high-grade osteosarcoma have been significantly improved in the past 30 years. However, 30-40% of primary non-metastatic osteosarcoma patients will suffer from distant metastasis. Although these patients have undergone resection of metastases, the prognosis is still very poor. The

total 5-year survival rate of patients with primary resectable metastases is 20%-30%, which tends to be 0 in patients with primary unresectable metastases.

Young patients with recurrent/metastatic osteosarcoma tend to have good physical conditions for second-line treatment. Currently, there is no high-level evidence-based second-line therapeutic regimen. The most common second-line chemotherapy regimens are as follows: First, for docetaxel and gemcitabine regimen, the effective rate (PR+SD) was 29%. Second, for cyclophosphamide and etoposide regimen, the 4-month disease-free survival rate and 1-year survival rate were 42% and 50%, respectively. Third, Ewing's sarcoma and rhabdomyosarcoma responded well to cyclophosphamide and topotecan regimen, while osteosarcoma was not sensitive to this regimen. Fourth, for high-dose intensive ifosfamide and etoposide regimen, the objective response rate was 30.8%. Fifth, for irinotecan with or without temozolomide regimen, the objective response rate was 30-60 in sarcoma, but less than 30% in osteosarcoma. The efficacy of conventional second-line therapeutic regimens was quite limited. Therefore, it is of vital importance to explore effective drugs which will bring new life to these patients in the second-line setting.

